### 7.2 Subject disposition

Subject disposition information will be summarized by treatment group, age stratum, race, ethnicity, sex at birth, country, and overall. A CONSORT diagram will be constructed that details the number of subjects screened, the number enrolled and eligible for vaccination, the number randomized to each trial arm, the number receiving the first and second vaccination, the number of early terminations, the number completing the study, and the number eligible for analysis.

The primary reason for early withdrawal will also be tabulated.

The number of subjects randomized will be used as the denominator for the proportion calculation. Subject disposition will be listed along with inclusion or exclusion criteria that were not met for randomization.

The number and percent of subjects in each analysis set will also be tabulated. A listing of each subject excluded from an analysis population will be listed as well as the reason why they were excluded from the population.

Treatment misallocations occur when a subject received a different treatment than they were randomized to. In these cases:

- If a subject was randomized but not treated, then the subject will be included with their randomized treatment group the subject disposition summaries. These subjects will be included in the ITT population only.
- If a subject was treated but not randomized, then by definition the subject will be excluded from the immunogenicity analyses since randomized treatment is missing but will be included in the ITT population and in the Safety population according to the treatment actually received for all safety analyses.

- If a subject was randomized but received a different treatment regimen, then the subject will be included according to their randomized treatment group for all immunogenicity analyses in the ITT/mITT population but will be excluded from immunogenicity analyses in the PP population. These subjects will be included according to the treatment regimen actually received for all safety analyses.

### 7.3 Protocol deviations/violations

The number of patients excluded from ITT, mITT, Safety, and Per-protocol analysis sets and reasons for exclusion will be summarized by treatment group and overall. Population membership details will be listed, including reason for exclusion from each population (on randomized subjects).

Protocol deviations will also be listed.

### 7.4 Demographics and baseline characteristics

#### 7.4.1 Demographics

Age at consent, height, weight, and other continuous demographic variables at baseline will be summarized descriptively. Sex, primary race, ethnicity, and other categorical variables will be summarized using the ITT and PP populations.

#### 7.4.2 Medical history

Medical history will be listed.

#### 7.4.3 Prior and concomitant medications

Data for all prior and concomitant medications will be summarized with percentages by treatment arm, for the ITT and PP populations.

Prior and concomitant medications will also be listed.

### 7.5 Extent of exposure

#### 7.5.1 Treatment duration

Study treatment exposure will be summarized as the number of subjects receiving a total of 1 and 2 doses of product and will be presented by treatment group on the ITT, mITT, PP, and safety populations.

#### 7.5.2 Treatment compliance

A full course of study product administration consists of two doses of vaccine. A summary table detailing the total number of doses received will be presented along with the reason a dose was not administered or missed. A summary of subjects receiving the dose outside the dosing window, 25 to 31 days post first dose, will be presented.

### 7.6 Immunogenicity analysis

## Statistical Analysis Plan (SAP) - Phase 2 Segment

---

The immunogenicity analyses will be performed using the PP population. Valid samples for statistical analysis purposes will include those collected at least 6 and no more than 30 days after Dose 2 for the Week 6 timepoint; at least 174 and no more than 198 days after Dose 2 for the Week 30 timepoint; and at least 356 and no more than 380 days after Dose 2 for the Week 56 timepoint. Baseline is defined as the last measurement prior to the first treatment administration.

The analyses will be stratified according to NP positive/negative status of the subjects, prior receipt of any non-study prophylactic COVID-19 vaccine of the subjects, and age group. Strata for age group are 18 – 50, 51+ and 65+ years at Dose 1. Strata for NP status are positive and negative at each time point (week 6, week 30, and week 56). Strata for prior receipt of any non-study prophylactic COVID-19 vaccine are yes and no at each time point. Additionally, a composite stratification of NP positive or non-study vaccinated and NP negative and not non-study vaccinated will be utilized.

At each post baseline time point, post-baseline increase from baseline in interferon- $\gamma$  ELISpot magnitude and post baseline increase from baseline in cellular immune magnitude measured by flow cytometry will be summarized using the median by treatment group. Differences in medians and associated nonparametric 95% CIs between treatment groups will be calculated.

The following sample of SAS code will be used to construct these confidence intervals.

```
proc npar1way hl alpha=.05 data=<DATASET>;
  class armcd;
  var <OUTCOME>;
  exact hl;
  ods select HodgesLehmann;
run;
```

In above SAS codes:

- Armcd represents active treatment and placebo, i.e., 1.0 mg INO-4800, 1injection placebo, or 2.0 mg INO-4800, and 2 injections placebo.
- OUTCOME represents interferon- $\gamma$  ELISpot or flow cytometry increases from baseline.
- hl adds Hodges-Lehmann confidence interval for location differences between treatment groups.

At each post baseline time point, post-baseline changes in neutralizing antibody (PRNT50) titers from ELISA will be summarized with GMFRs by treatment group. The GMFRs will be compared between treatment groups using ratios and associated 95% t-distribution based CIs.

The following sample of SAS code will be used to construct these confidence intervals.

```
proc mixed data=<DATASET>;
  class armcd(ref='xx');
  model LR = armcd;
  lsmeans armcd / cl diff alpha=0.05;
  ods output diff=diff;
run;
```

```
data diff1; set diff;
  GMFR=10**(Estimate);
  Lclm=10** (lower);
  Uclm=10** (upper);
run;
```

In above SAS codes:

- Armcd represents active treatment and placebo, i.e., 1.0 mg INO-4800, 1 injection placebo, or 2.0 mg INO-4800, and 2 injections placebo.
- LR represents  $\log_{10} Y_i / B_i$ , where  $Y_i$  is the post dose assay result for subject  $i$ ; and  $B_i$  is the baseline assay result for subject  $i$ .
- xx represents reference arm (i.e., 1 injection placebo or 2 injection placebo or 1.0 mg INO-4800 or 2.0 mg INO-4800)

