### **3 Study Endpoints**

#### **3.1 Primary endpoints**

- Antigen-specific cellular immune response measured by IFN-gamma ELISpot
- Neutralizing antibody response measured by a pseudovirus-based neutralization assay

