## 7 Statistical Methods

### 7.1 General statistical conventions

All statistical procedures will be completed using SAS version 9.4 or higher.

Unless otherwise stated, all statistical testing will be two-sided and will be performed using a significance (alpha) of 0.05. Two-sided 95% confidence intervals (CI) will be provided when relevant.

Continuous variables will be summarized using descriptive statistics, including number of subjects (n), mean, median, standard deviation (SD), minimum, and maximum. Means and medians will be rounded to one more

decimal place than what is reported in the data. Standard deviations will be rounded to two more decimal places than what is reported in the data.

For categorical variables, summaries will include counts of subjects and percentages. Percentages will be rounded to one decimal place.

For summary purposes, baseline is defined as the last measurement prior to the first treatment administration. All summaries will be presented by treatment group, unless otherwise specified.

All subject data, including those derived, will be presented in individual subject data listings. Unless otherwise stated, unscheduled visit results will be included in date/time chronological order, within patient listings. All listings will be sorted by investigational site, subject ID, date/time and visit. The treatment group as well as the patient's sex and age will be stated on each listing. Unless otherwise stated, data listings will be based on all subjects randomized (ITT Population).

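### Phase 2 ELISpot and flow cytometry: the between-group estimate is a difference in medians, but its 95% interval comes from the Hodges-Lehmann procedure, which targets a different quantity unless the arms differ by a pure shift

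*SAP*

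**What the plan says.** Section 3.1 of the Phase 2 SAP lists the cellular response as one of two primary endpoints: "Antigen-specific cellular immune response measured by IFN-gamma ELISpot". Flow cytometry is exploratory (Section 3.3).

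Section 7.6 says that at each post-baseline time point the increase from baseline on both assays "will be summarized using the median by treatment group". For the comparison it adds: "Differences in medians and associated nonparametric 95% CIs between treatment groups will be calculated". It then introduces the code: "The following sample of SAS code will be used to construct these confidence intervals". That code is PROC NPAR1WAY with the `hl` option, an exact request, and an ODS statement selecting the HodgesLehmann table. The note to the code reads: "hl adds Hodges-Lehmann confidence interval for location differences between treatment groups".

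The section does not assume a pure shift between arms. It does not say that the Hodges-Lehmann estimate stands in for the difference between the two arm medians.

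**The concern.** The sentence on the estimate and the code for the interval name two different targets:

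- **Difference in medians:** median(X) − median(Y), with X and Y the increases in the two arms.
- **Hodges-Lehmann shift:** median of X − Y over all pairs of one subject from each arm.

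Two statisticians following Section 7.6 could report different point estimates for a primary endpoint. One would subtract the arm medians and attach the Hodges-Lehmann limits. The other would copy the estimate from the Hodges-Lehmann table and call it a difference in medians. The first risks an estimate outside its own interval. The second mislabels the estimate, which need not match the arm medians shown next to it.

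Phase 2 has no powered test (Section 4), so type I error is not at issue. What matters is that the estimate and its interval are the result, and Section 2.5 bases Phase 3 dose selection on Week 6 immunogenicity together with Week 8 safety.

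**Working it through.** The SAP states no figure on this point, so there is none to reproduce.

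**Inputs from the SAP.** Arms of 150, 150, 50 and 50 (Section 2.5, Table 1); two-sided 95% intervals (Section 7.1); Hodges-Lehmann interval (Section 7.6). All outcome distributions below are assumptions.

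**When the targets agree.** If X has the distribution of Y + c, both equal c. They also agree if both distributions are symmetric. Neither condition is stated, and neither holds in general if only some vaccinees respond.

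**That the estimate can fall outside the interval.** Take a constructed sample of 150 versus 50:

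- Arm 1: 80 values evenly spaced from −5 to 5, and 70 from 20 to 300. Arm 2: 50 values evenly spaced from −20 to 20.
- The median of arm 1 is the mean of its 75th and 76th values: (4.367 + 4.494)/2 = 4.43. The median of arm 2 is 0. The difference in medians is 4.43.
- Large-sample Wilcoxon cut-off: mn/2 − 1.96 × √(mn(m+n+1)/12) = 3750 − 1.96 × √(7500 × 201/12) = 3750 − 694.7, rounded down to 3055. The limits are the 3055th and 4446th of the 7500 ordered differences.
- Result: Hodges-Lehmann estimate 17.47, 95% CI 10.51 to 54.39. The value 4.43 lies outside.

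**Why a responder mixture separates the targets.** Let a share p respond (lognormal, median 40, log-SD 1) and the rest be normal with mean 0 and SD 4. The arm median M solves (1 − p)Φ(M/4) + pΦ(ln(M/40)) = 0.5.

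- p = 0.65: Φ(M/4) is about 1, so Φ(ln(M/40)) = 0.15/0.65 = 0.231, ln(M/40) = −0.736, M = 19.2.
- p = 0.50: M = 7.0, since Φ(1.75) + Φ(−1.74) is about 0.960 + 0.041 = 1.00.
- Difference in medians: 19.2 − 7.0 = 12.2. The Hodges-Lehmann shift for the same arms is 4.7 by simulation.

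Near a 50% response rate the arm median sits in the sparse region between non-responders and responders, so it moves a long way for a modest change in p.

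**How often it matters.** Several hundred to 2,000 simulated trials per scenario, with the large-sample interval where the SAP asks for the exact one. *Outside* means that the observed difference in medians lies outside the Hodges-Lehmann interval. *Coverage* is of the true difference in medians.

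| Scenario (assumed) | n | True difference in medians | True HL shift | Outside | Coverage |
|---|---|---|---|---|---|
| Normal, pure shift of 0.5 SD | 150/50 | 0.50 | 0.50 | 0.1% | 0.956 |
| Lognormal, pure shift | 150/50 | 0.50 | 0.50 | 0.3% | 0.945 |
| Active v placebo, 30% to 90% responders (median 40), noise SD 4 in both arms | 150/50 | varies | varies | 0% to 0.8% | 0.89 to 0.98 |
| Active v placebo, 45% responders (median 60), noise SD 5 in both arms | 150/50 | 6.36 | 8.34 | 0.4% | 0.909 |
| As above, but placebo SD 10 | 150/50 | 6.31 | 11.47 | 34.7% | 0.530 |
| Dose v dose, 65% v 50% responders (median 40), noise SD 4 | 150/150 | 12.2 | 4.7 | 70% | 0.31 |
| Dose v dose, 75% v 55% responders, noise SD 4 | 150/150 | 15.3 | 8.3 | 46% | 0.50 |
| Dose v dose, 65% v 50% responders, noise SD 10 | 150/150 | – | – | 0.2% to 0.6% | 0.93 to 0.94 |

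In the continuous scenarios where it was recorded, the Hodges-Lehmann interval covered its own target in about 94% to 98.5% of trials. The interval is sound for its own target; the stated estimate is what does not match it.

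**The case against.** Three arguments carry weight.

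1. **The selected table already contains a matching estimate.** The HodgesLehmann output holds the estimate and its limits, and the code note speaks of location differences. If the programmer reports that table, nothing falls outside anything. This stands as a limit on the harm: the contradiction appears only if the arm medians are subtracted separately. The text still calls the result a difference in medians, so it needs correcting on either reading.

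2. **The severe figures come from dose versus dose.** The note to the Hodges-Lehmann code lists each INO-4800 dose with its own placebo. Either dose as a reference arm appears only in the note to the PROC MIXED antibody code. For ELISpot, dose versus dose follows only from the general reference to treatment groups. For active versus placebo with equal noise the problem is nearly absent. It becomes large there only if placebo noise is assumed to exceed that of vaccinated non-responders, which nothing in the SAP supports.

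3. **The dose-versus-dose result is fragile.** It needs response rates near 50% and tight noise. At SD 4, 30% v 35% responders gives 0.2% outside, 80% v 90% gives 1.0%, and 70% v 85% gives 2.3%.

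It is also true that no stated dose-selection rule uses this interval. Version 2.0 is dated 20 January 2022, and its Section 7.8 treats data collection for dose selection as complete.

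A reader might infer that the planned interval lacks 95% coverage outright, or that the results table will contradict itself. The SAP does not support that: it gives no ELISpot distribution, and the simulated frequency runs from 0% to over 99% depending on what is assumed.

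**Conclusion.** The point stands in a limited form. Section 7.6 names one between-group quantity and constructs an interval for another, on a primary endpoint and on flow cytometry. That mismatch is in the text and needs no assumption. Its numerical effect does: negligible under a pure shift or for active versus placebo with equal noise, and severe in some dose-versus-dose mixtures. Which applies here cannot be determined from the SAP. The correction is worth making because the estimate is left open to two readings and settling it costs little. It is not evidence that any dose comparison was wrong.

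**What to change.** In Section 7.6, make the between-group estimate for ELISpot and flow cytometry the Hodges-Lehmann estimate from the specified code, with its Hodges-Lehmann 95% interval. Label it 'Hodges-Lehmann location shift (median of pairwise differences)' and keep the arm medians as descriptive summaries. State which pairs of arms are compared, and in particular whether dose versus dose is included.

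This changes SAP wording and table labels only, since the code already prints the estimate. The downside is that the reported shift need not equal the difference between the two displayed arm medians, so the table needs a footnote saying so.

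If the difference in medians is preferred as the estimate, replace the interval with one built for it, for example a percentile bootstrap resampling within arm, with the number of replicates and the seed fixed in advance. That needs new code in place of the PROC NPAR1WAY step.

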## Statistical Analysis Plan (SAP) - Phase 2 Segment

In the Phase 2 segment, approximately 400 subjects 18 years of age and older will be randomized at a 3:3:1:1 ratio across four dose groups (Table 1).

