## Statistical Analysis Plan (SAP) - Phase 2 Segment

- a. Screening assessment occurs from -30 days to -1 day of Day 0.
- b. Full physical examination only at Screening and Day 393 (or EOS). Targeted physical exam at other indicated visits.
- c. Hemoglobin A1c collected at screening only. Chemistry includes Na, K, Cl, HCO3, Ca, PO4, glucose, BUN, Cr, alkaline phosphatase, AST, ALT, LDH, total bilirubin.
- d. Dipstick for glucose, protein, and hematuria. Microscopic examination should be performed if dipstick is abnormal.
- e. Serum pregnancy test at Screening. Urine pregnancy test at other visits.
- f. Intradermal injection(s) in skin preferably over deltoid muscle, or alternately over anterolateral quadriceps muscle, followed by EP at Day 0 and Day 28.
- g. Following administration of INO-4800 or placebo, EP data will be downloaded from the CELLECTRA® 2000 device and provided to Inovio.
- h. AEs to be collected from time of consent to Day 56; SAEs, MAAEs, and AESIs to be collected from time of consent to EOS.
- i. On Day 0, cellular sampling requires 64 mL of whole blood (8 Cell Preparation Tubes (CPT), each 8 mL of whole blood) prior to 1st dose. At all other time points, collect 32 mL of whole blood (4 CPT tubes, each 8 mL of whole blood).
- j. On Day 0, humoral sampling requires a total of 17 mL of whole blood (two 10-mL red top serum collection tubes, each 8.5 mL of whole blood, to produce eight serum aliquots of 1 mL each). At all other time points, collect 8.5 mL of whole blood in a single 10-mL red top serum collection tube to produce four serum aliquots of 1 mL each.
- k. SARS-CoV-2 antibody.
- l. Saliva specimen at Screening; Nasal swab and saliva specimens at COVID-19 assessment and convalescent visits. Genotyping may also be performed on sample(s) collected at the COVID-19 assessment visit.
- m. Subjects will be evaluated during a "COVID-19 assessment visit" when acute COVID-19 is suspected. The assessment visit may be performed in the clinic, in the subject's vehicle or at the subject's home and should be completed within 3 days of symptom onset or within 3 days of a positive result of a SARS-CoV-2 test.

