### **4 Sample Size and Power**

The phase 2 segment of this trial was not powered to conduct any formal hypothesis testing.

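### Phase 2 neutralizing antibody model fixes the slope on the Day 0 log titre at 1 instead of estimating it: a valid analysis that may carry avoidable variance

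*SAP*

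**What the plan says.** Neutralizing antibody response is one of the two Phase 2 primary endpoints (Phase 2 SAP, section 3.1). Section 7.6 states: "The GMFRs will be compared between treatment groups using ratios and associated 95% t-distribution based CIs". The sample code fits "model LR = armcd" in PROC MIXED and back-transforms the arm differences. LR is log10(Yi/Bi), and Bi "is the baseline assay result for subject" i.

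The baseline value exists for this purpose. "Baseline is defined as the last measurement prior to the first treatment administration" (section 7.6), and the notes to the schedule of events provide the sample: "On Day 0, humoral sampling requires a total of 17 mL of whole blood".

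Subjects are "randomized at a 3:3:1:1 ratio across four dose groups", expected to be 150, 150, 50 and 50 (Table 1), without stratification (section 2.6). Section 7.6 repeats the analyses by NP status, non-study vaccination and age group. Baseline titre is not among these strata. On precision, section 4 says: "The phase 2 segment of this trial was not powered to conduct any formal hypothesis testing".

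**The concern.** Modelling log10(Yi/Bi) on arm alone is the same as modelling log10 Yi with the coefficient of log10 Bi set to 1. That is the best value only if a subject whose Day 0 log titre is one unit higher also has a post-dose log titre one unit higher. If Day 0 values in a largely seronegative population are mostly assay noise, the true slope is nearer 0, and subtracting baseline puts its noise into every fold rise.

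The Phase 2 comparison is read through its confidence intervals, since no formal test is powered. The placebo arms have 50 subjects each, and Week 6 immunogenicity feeds the Phase 3 dose selection (section 2.5). At stake are the width of those intervals and their sensitivity to a chance difference in Day 0 titres between arms.

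**Working it through.** **Inputs from the SAP.** Arms: 400 × 3/8 = 150 and 400 × 1/8 = 50, which agrees with Table 1. Intervals are two-sided 95% and t-based. The SAP states no SD, correlation, assay limit or interval width for this endpoint, so there is no planned figure to reproduce.

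**Assumed inputs.** sY is the post-dose SD of log10 titre, sB the baseline SD, ρ their correlation and r = sB/sY. None of these is in the documents.

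**Step 1: variance with a common slope.**
- Fold-rise model, per subject: sY² + sB² − 2ρ·sY·sB.
- Estimated slope: sY²(1 − ρ²).
- Difference: (sB − ρ·sY)². It is zero when ρ = r, which means a slope of exactly 1. With a constant baseline both models coincide.

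SE with an estimated slope relative to the SAP model = √[(1 − ρ²)/(1 + r² − 2ρr)]:

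| r | ρ = 0 | ρ = 0.2 | ρ = 0.4 | ρ = 0.5 |
|---|---|---|---|---|
| 0.1 | 0.995 | 0.995 | 0.950 | 0.908 |
| 0.25 | 0.970 | 0.999 | 0.987 | 0.961 |
| 0.5 | 0.894 | 0.956 | 0.994 | 1.000 |
| 0.75 | 0.800 | 0.872 | 0.934 | 0.961 |
| 1 | 0.707 | 0.775 | 0.837 | 0.866 |

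The gain is 4% at r = 0.5, ρ = 0.2 and 23% at r = 1, ρ = 0.2. Over the whole block r = 0.5–1, ρ = 0–0.4 it runs from 0.6% to 29%.

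Example with sY = sB = 0.5 and ρ = 0.2, 150 vs 50. The SAP model variance is 0.25 + 0.25 − 0.10 = 0.40, so the half-width is 1.966 × √(0.40 × (1/150 + 1/50)) = 0.203 log10, a factor of 1.60. With an estimated slope the variance is 0.24 and the factor 1.44.

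**Step 2: simulation** (2,000 runs per scenario, 150 vs 50, true log10 difference 0.40). Both models averaged 0.397 to 0.402, with coverage of 94% to 96%. The ratio of interval widths was 1.00 with all baselines at one value, 0.995–0.996 with 5–10% detectable, 0.96 with 30% detectable, and 0.87 with all baselines variable and ρ = 0.5.

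**Step 3: chance imbalance.** A baseline difference d between arms shifts the log ratio by (slope − 1)·d. With assumed sB = 0.25, one SD of d is 0.25 × √(1/150 + 1/50) = 0.041. At slope 0 that moves the ratio by a factor of 10^0.041 = 1.10.

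**Step 4: slopes that differ by arm.** Assume slope 0 and residual SD 0.5 on vaccine, slope 1 and residual SD 0.15 on placebo, and sB = 0.5. Large-sample variance of the arm difference:
- SAP model: (0.25 + 1² × 0.25)/150 + 0.0225/50 = 0.00378, SE 0.0615.
- One common slope, 0.75 × 0 + 0.25 × 1 = 0.25: (0.25 + 0.25² × 0.25)/150 + (0.0225 + 0.75² × 0.25)/50 = 0.00503, SE 0.0709.
- Separate slopes, centred baseline: 0.25/150 + 0.0225/50 + (1 − 0)² × 0.25/200 = 0.00337, SE 0.0580.

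Relative to the SAP model, the common slope is worse (1.15) and separate slopes are better (0.94). With sB = 0.25 the same sums give 1.06 and 0.98. Simulation agrees: 1.07–1.17 and 0.95–0.98.

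**The case against.** The strongest reply is that nothing here is wrong. The plan announces ratios of fold rises with t-based intervals, and the code delivers them. Both models are unbiased, and no power or precision target is missed. A reader might infer that the plan ignores the Day 0 titre. It does not: the titre is the denominator of every fold rise, and only the estimation of its slope is absent. Nor does all baseline noise reach the interval, because the excess vanishes at slope 1 or with a constant baseline. In a population described as seronegative, many baselines may sit at one value, and the gain may then be negligible. All of this stands.

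A second objection concerns the remedy. A reader might infer that adding a baseline covariate can never cost precision. That holds in large samples when slope and residual variance are the same in both arms. With 150 against 50, and vaccine compared with placebo, equal slopes are not a safe assumption. A single common slope is weighted towards the large arm and can do worse than the fixed slope of 1 (Step 4). It can also do so while the software reports a smaller SE: in simulations of such cases the reported SE fell to 0.79–0.95 of the SAP model's while the true SE rose to 1.02–1.17. This objection also stands, and it is why the fix includes an arm-by-baseline term.

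What survives is that small Day 0 variation cannot be taken for granted. The SAP gives no baseline distribution, and Phase 2 serology is scheduled only at Screening, up to 30 days before Day 0.

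**Conclusion.** The point holds as a minor efficiency suggestion. The Phase 2 model is valid and unbiased, but it fixes a slope that the existing data could estimate. The possible cost is a wider interval and a ratio that moves with chance baseline imbalance.

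The size is unknown: nothing if baselines are constant or the slope is 1, about 0.5% if 5–10% of baselines are detectable, and about 4% to 23% of the SE at the assumed combinations picked out in Step 1. All of these rest on assumed SDs and correlations. The documents do not support reading the current analysis as biased, or the loss as known to be material.

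**What to change.** In section 7.6, add the mean-centred log10 baseline titre and its interaction with arm: `model LR = armcd clogB armcd*clogB;`. Report the back-transformed arm difference at the mean baseline. Because LR already contains the baseline, the target remains the ratio of fold rises. Keep unadjusted GMFRs by arm as descriptive statistics.

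Use a variance that does not assume equal residual spread, for example a separate residual variance per arm with Satterthwaite degrees of freedom. Allow also for the estimated centring value: add (slope difference)² × sB²/N, or bootstrap. In Step 4 this term is 0.00125 of 0.00337; without it the SE would read 0.0460 instead of 0.0580.

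State that the model reverts to the current one where baseline is constant. Also set a minimum number of non-constant baselines per arm: with 5% detectable, a placebo arm of 50 has only 2 or 3 such subjects, too few for its own slope. The same rule covers small strata.

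The cost is two degrees of freedom in a two-arm fit (four if all arms share one model) and a few lines of code, with no new data. If the current model is kept as the main analysis, this one can be pre-specified as a sensitivity analysis.
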